### **3.7 Discontinuation of the study**

Those patients who had not symptom relief after four weeks of esomeprazole would discontinue this study.

## **4. STUDY PLAN AND TIMING OF PROCEDURES**

The study includes screening and treatment period. The screen period would be 7 days, during this stage all the procedure including questionnaires, upper endoscopy and MII-pH monitoring need to be finished. The treatment period would be 4 to 8 weeks according to the findings under upper endoscopy. For patients with esophagitis, this period would be 8 weeks; for patients with normal findings, this period would be 4 weeks.

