### **3.1 Inclusion criteria**

1. Consecutive patients aged 18–65 years who go to the gastroenterology clinic presented with upper gastrointestinal discomfort, such as the following symptoms: heartburn, regurgitation, dysphagia, substernal pain, epigastric pain, epigastric burning, early satiety, postprandial fullness.
2. The previous symptoms should last for at least 3 months.
3. The frequency of the previous symptoms should be at least 3 days per week with at least moderate.
4. All the previous symptoms would be evaluated in the questionnaires (see attachment).

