### **3.5 Methods for ensuring blinding**

Not applicable. This is a cross-sectional study.

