**Table 1 Study Plan detailing the procedures for patients with esophagitis**

Visit	1	2	3	4	5	6	7
Visit window	Screening						
Days -7 to 0 for Visit 1							
±0 day for Visit 2							
±1 day for Visits 3 and 4							
±5 days starting at Visit 5							
Week		0	1	2	4	8	12
Day	-	0	7	14	28	56	84
Written informed consent (including tissue samples, pharmacogenetics)	X						
Demographics	X						
Physical examination, height, and weight	X						
Medical/surgical history	X						
Inclusion/exclusion criteria	X	X					
Treatment dispensed/returned		X					X
Concomitant medication	X	X	X	X	X	X	X
GERD questionnaire		X	X	X	X	X	X

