**Table 2 Study Plan detailing the procedures for endoscopy negative patients**

Visit	1	2	3	4	5	6
Visit window	Screening					
Days -7 to 0 for Visit 1						
±0 day for Visit 2						
±1 day for Visits 3 and 4						
±5 days starting at Visit 5						
Week		0	1	2	4	8
Day	-	0	7	14	28	56
Written informed consent (including tissue samples, pharmacogenetics)	X					
Demographics	X					
Physical examination, height, and weight	X					
Medical/surgical history	X					
Inclusion/exclusion criteria	X	X				
Treatment dispensed/returned		X				
Concomitant medication	X	X	X	X	X	X
GERD questionnaire		X	X	X	X	X

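### Section 4 and Tables 1 and 2 disagree on when the questionnaire is given, and nothing requires it to come before endoscopy and pH monitoring

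*Combined protocol and SAP*

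**What the plan says.** Section 4 describes a 7-day screening period and states that "during this stage all the procedure including questionnaires, upper endoscopy and MII-pH monitoring need to be finished". It does not say which of the three comes first.

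Tables 1 and 2 have one questionnaire row each, "GERD questionnaire". In both tables it is blank at Visit 1 (screening, "Days -7 to 0 for Visit 1") and first marked at Visit 2, which is Day 0 with no tolerance (the window line reads ±"0 day for Visit 2"). Treatment is dispensed at that same visit. Neither table has a row for endoscopy, MII-pH monitoring or SF-36. The tables are divided by endoscopic finding: "Study Plan detailing the procedures for patients with esophagitis" and "Study Plan detailing the procedures for endoscopy negative patients".

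On eligibility, Section 3.1 sets frequency and severity thresholds (criterion 3) and adds as criterion 4: "All the previous symptoms would be evaluated in the questionnaires (see attachment"). Both tables tick the inclusion/exclusion check at Visits 1 and 2.

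Section 7.4.1 takes the primary result from the symptom questionnaire: the symptom with the highest percentage is named the primary symptom. Section 7.4.2 evaluates GerdQ against pH monitoring or endoscopy. On blinding, Section 3.5 says only: "Not applicable. This is a cross-sectional study".

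**The concern.** The primary endpoint depends on what patients call their symptoms. Section 1.1 argues that Chinese has no direct term for heartburn and that patients describe the sensation in other words, so the labels are likely to be easy to influence. A patient who has just heard that reflux or esophagitis was found, or a clinician who knows it, may settle on a reflux term that would not have been chosen a few days earlier. Section 7.4.1 names whichever symptom ranks first, with no margin, so a modest shift in labelling could matter if the leading symptoms are close.

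GerdQ raises the same problem as a test-accuracy question. If it is answered with the reference result known, its agreement with pH monitoring or endoscopy is no longer an independent comparison and would probably look better than it is.

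There is also a practical gap. The first symptom-eligibility check falls at a visit with no questionnaire scheduled. Unless clinic history fills that role, some patients could have an endoscopy and a 24-hour catheter study before the form that describes their symptoms is completed.

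**Working it through.** The point rests on comparing sections. No figure in the plan measures it.

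**1. When is the questionnaire given?**

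| Source | Questionnaire timing | Endoscopy and pH timing |
|---|---|---|
| Section 4 | Within the 7-day screening period | Within the same period, no order |
| Table 1 | Blank at Visit 1; marked at Visits 2 to 7 (Days 0, 7, 14, 28, 56, 84) | Not listed |
| Table 2 | Blank at Visit 1; marked at Visits 2 to 6 (Days 0, 7, 14, 28, 56) | Not listed |

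Neither table marks the questionnaire at Visit 1, and both first mark it at Day 0. This does not match Section 4, except in so far as the Visit 1 window itself runs up to Day 0.

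**2. What is known by Day 0?**

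- *Endoscopy.* The result must be known. Exclusion criterion 1 (Section 3.2) depends on it, and so does the choice between Table 1 and Table 2.
- *pH monitoring.* The result is probably known. Section 4 requires the recording to be finished in screening, and a 24-hour recording finished by Day 0 has to start before it. Section 1.2 gives esomeprazole to patients without a positive pH finding, which needs a result before the Visit 2 dispensing, and Section 7.3 also places treatment after the pH definition. Against this, Section 3.4 assigns treatment by endoscopic finding, and the synopsis speaks of endoscopy or pH monitoring. The pH step is therefore a supported inference and not a stated fact.

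**3. Is there any safeguard?** No section puts the symptom questionnaire or GerdQ first, and none keeps patients or staff unaware of results while the forms are completed. Under the tables the questionnaire follows endoscopy. Under Section 4 the order is open.

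**4. Who is exposed?** Section 7.3 defines GERD by pH monitoring, endoscopy or a positive PPI test. The PPI test is read in the fourth week, so patients positive on that test alone are not known as cases at Day 0. Those who could hear of a positive finding before answering are therefore a subset of the GERD cases.

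**5. Scale.** The plan's only precision figure reproduces: 1.96 × √(0.30 × 0.70 / 400) = 0.0449, stated as 0.045. The same inputs give 400 × 0.30 = 120 GERD cases. Each patient who changes a label moves that symptom's percentage by 1/120 = 0.83 points. If one symptom is swapped for another, the gap between them moves by 2/120 = 1.67 points. For comparison, the 95% half-width for a symptom reported by half of 120 cases is 1.96 × √(0.50 × 0.50 / 120) = 0.089. The documents give neither the number of patients who would change a label nor the expected gap between the leading symptoms, so the calculation stops here.

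**The case against.** The strongest reply is that the tables are visibly incomplete. They omit endoscopy, pH monitoring and SF-36, all of which the protocol requires, so a missing mark at Visit 1 is weak evidence that no questionnaire is given in screening, where Section 4 expressly puts it. The row name also does not settle the instrument. Elsewhere the protocol speaks of a symptom questionnaire, GerdQ, SF-36 and attached questionnaires, and a row repeated through treatment and follow-up would also suit serial scoring for the PPI test. Finally, eligibility is ticked again at Visit 2, alongside the questionnaire; history is taken at Visit 1; and Section 3.6 withdraws patients whose symptoms do not meet the criteria.

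Much of this stands. A reader might infer that the protocol schedules the primary-endpoint questionnaire after both results are available. The documents do not say so: Section 4 points the other way, the tests are absent from the tables, and disclosure of the pH result by Day 0 is inferred. A reader might also infer that questionnaire-based eligibility is only ever decided after the tests. The Visit 2 check makes that possible but not established, because Section 3.1 does not make the questionnaire the sole basis for eligibility.

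The reply does not remove the contradiction or supply a safeguard. If the row is not the symptom questionnaire, then that instrument appears in neither table, which also needs correcting.

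**Conclusion.** The point holds as a conflict between Section 4 and Tables 1 and 2, together with an unspecified order that leaves the primary endpoint open to an avoidable bias. It should be corrected.

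The bias argument rests on three assumptions: that "GERD questionnaire" is, or includes, the symptom questionnaire (and GerdQ, for the accuracy analysis); that sites follow the tables; and that results are known to the patient or clinician when the form is completed. The last is secure for the clinical team on endoscopy and probable for pH.

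The size cannot be derived. A reader might assume that some percentage of all 120 GERD cases would change a label and conclude that the named symptom would change. The documents do not support this. They give no relabelling rate, the exposed group excludes cases found only by the PPI test, a full gap shift needs swaps in one direction between the same two symptoms, and no expected gap is stated. The direction of the effect on GerdQ accuracy, probably upward, is likewise a judgement and not a result.

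**What to change.** Reconcile Section 4 with Tables 1 and 2:

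- Name each instrument in the tables in place of the single generic row, and add rows for endoscopy and MII-pH monitoring so that the order is visible.
- Mark the symptom questionnaire and GerdQ at Visit 1, and state in Section 4 that both are completed after consent and before endoscopy and MII-pH monitoring.
- State that this Visit 1 record is used for inclusion criteria 3 and 4, the symptom percentages in Section 7.4.1 and the GerdQ analysis in Section 7.4.2.
- Keep the Day 0 questionnaire as the baseline for the PPI-test score.

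The cost is an amendment to the text and two tables, and one further completion of existing forms at an existing visit. The downside is a few extra minutes at Visit 1.

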**Table 1 Study Plan detailing the procedures for patients with esophagitis**

Visit	1	2	3	4	5	6	7
Visit window	Screening						
Days -7 to 0 for Visit 1							
±0 day for Visit 2							
±1 day for Visits 3 and 4							
±5 days starting at Visit 5							
Week		0	1	2	4	8	12
Day	-	0	7	14	28	56	84
Written informed consent (including tissue samples, pharmacogenetics)	X						
Demographics	X						
Physical examination, height, and weight	X						
Medical/surgical history	X						
Inclusion/exclusion criteria	X	X					
Treatment dispensed/returned		X					X
Concomitant medication	X	X	X	X	X	X	X
GERD questionnaire		X	X	X	X	X	X

**Table 2 Study Plan detailing the procedures for endoscopy negative patients**

Visit	1	2	3	4	5	6
Visit window	Screening					
Days -7 to 0 for Visit 1						
±0 day for Visit 2						
±1 day for Visits 3 and 4						
±5 days starting at Visit 5						
Week		0	1	2	4	8
Day	-	0	7	14	28	56
Written informed consent (including tissue samples, pharmacogenetics)	X					
Demographics	X					
Physical examination, height, and weight	X					
Medical/surgical history	X					
Inclusion/exclusion criteria	X	X				
Treatment dispensed/returned		X				
Concomitant medication	X	X	X	X	X	X
GERD questionnaire		X	X	X	X	X

#### **4.1 Enrolment/screening period**

*Seven days*

#### **4.2 Treatment period**

Four to eight weeks

#### **4.3 Follow-up period**

Four weeks

### **5. SAFETY REPORTING AND MEDICAL MANAGEMENT**

The Principal Investigator is responsible for ensuring that all staff involved in the study are familiar with the content of this section.

#### **5.1 Definition**

##### **Adverse Events**

An adverse event is the development of an undesirable medical condition or the deterioration of a pre-existing medical condition following or during exposure to a pharmaceutical product, whether or not considered causally related to the product. An undesirable medical condition can be symptoms (e.g., nausea, chest pain), signs (e.g., tachycardia, enlarged liver) or the abnormal results of an investigation (e.g., laboratory findings, electrocardiogram). In clinical studies, an AE can include an undesirable medical condition occurring at any time, including run-in or washout periods, even if no study treatment has been administered.

The term AE is used to include both serious and non-serious AEs.

##### **Serious Adverse Event**

A serious adverse event is an AE occurring during any study phase (i.e., run-in, treatment, washout, follow-up), that fulfils one or more of the following criteria:

- Results in death
- Is immediately life-threatening
- Requires in-patient hospitalisation or prolongation of existing hospitalisation
- Results in persistent or significant disability/incapacity or substantial disruption of the ability to conduct normal life functions
- Is a congenital abnormality or birth defect
- Is an important medical event that may jeopardise the subject or may require medical intervention to prevent one of the outcomes listed above.

## **Adverse Drug Reaction (ADR)**

An ADR is a response to a medicinal product which is noxious and unintended. A response in this context means that a causal relationship between the medicinal product and an AE is at least a reasonable possibility.

### **5.2 Reporting of Serious Adverse Events**

Investigators are responsible for meeting all regulatory reporting requirements.

The investigator should report SAEs associated with AstraZeneca study drug Esomeprazole to AstraZeneca Patient Safety data entry site within 24 hours of initial awareness, whether or not considered causally related to the AstraZeneca investigational product.

For fatal or life-threatening adverse events where important or relevant information is missing, active follow-up is undertaken immediately. Investigator should inform AstraZeneca of any follow-up information on a previously reported SAE within one calendar day when he or she becomes aware of it.

### **5.3 Reporting of Non-serious Adverse Drug Reactions**

All non-serious ADRs which are suspected to be related to AstraZeneca investigational Product should be reported to AstraZeneca.

If any non-serious ADR occurs in the course of the study, the investigator should report it to AstraZeneca Patient Safety data entry site within 24 hours of initial awareness.

AstraZeneca Patient Safety data entry site contact information:

E-mail: [[contact]](mailto:[contact])

## **6. INVESTIGATIONAL PRODUCT AND OTHER TREATMENTS**

Esomeprazole MUPS, 20 mg, bid, Astrazeneca, 4- 8 weeks

## **7. STATISTICAL ANALYSES**

### **7.1 Sample size estimate**

Assuming the prevalence of GERD is 30%, 400 completed patients provides a precision (half width of 95% CI) of 0.045 for the estimate of two-sided 95% confidence interval of the primary endpoint..

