### **Statistical methods**

Assuming the prevalence of GERD is 30%, 400 completed patients provides a precision (half width of 95% CI) of 0.045 for the estimate of two-sided 95% confidence interval of the primary endpoint. All patients underwent upper endoscopy or an ambulatory 24-h pH monitoring. Pathologic esophageal acid reflux was defined as the percentage total time for which a pH value < 4 was >4.2 % in the distal esophagus. Then, patients were treated with esomeprazole 20 mg twice daily for 28 days. The symptom scores were measured by the frequency score multiplied by the severity scores of the predominant symptom before and at the end of the treatment, and the “ PPI test ” was defined as positive if the overall scores of the predominant dyspeptic symptom in the fourth week decreased by >50 % compared with those of the baseline.

Clinical Study Protocol  
Drug Substance Esomeprazole  
Study Code D9612L00157  
Edition 2.0  
Date Jun 8 2018

GERD is defined by either 24-hour impedance-pH monitoring or positive PPI test or positive result from endoscopy. The percentage of each symptom of GERD in the symptom questionnaire in Chinese outpatients in Gastroenterology department will be calculated. The symptom of the highest percentage will be the primary symptom.

	PAGE
TITLE PAGE .....	1
PROTOCOL SYNOPSIS.....	2
TABLE OF CONTENTS.....	5
1. INTRODUCTION .....	7
1.1 Background and rationale for conducting this study .....	7
1.2 Rationale for study design, doses and control groups.....	8
1.3 Study Design .....	9
2. STUDY OBJECTIVES.....	10
2.1 Primary objective .....	10
2.2 Secondary objectives.....	10
2.3 Safety objectives .....	10
3. SUBJECT SELECTION, ENROLMENT, RANDOMISATION, RESTRICTIONS, DISCONTINUATION AND WITHDRAWAL.....	10
3.1 Inclusion criteria .....	11
3.2 Exclusion criteria .....	11
3.3 Subject enrolment and randomization.....	11
3.4 Methods for assigning treatment groups .....	11
3.5 Methods for ensuring blinding.....	11
3.6 Criteria for withdrawal.....	12
3.7 Discontinuation of the study .....	12
4. STUDY PLAN AND TIMING OF PROCEDURES.....	12
4.1 Enrolment/screening period .....	15
4.2 Treatment period.....	15
4.3 Follow-up period.....	15
5. SAFETY REPORTING AND MEDICAL MANAGEMENT .....	15
5.1 Definition.....	15
Adverse Events.....	15
Serious Adverse Event.....	15
Adverse Drug Reaction (ADR) .....	16

5.2	Reporting of Serious Adverse Events.....	16

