## 2. STUDY OBJECTIVES

### 2.1 Primary objective

Primary Objective:	Outcome Measure:
To define the primary symptom of GERD in Chinese outpatients in Gastroenterology department	The primary symptoms of GERD in Chinese outpatients in Gastroenterology department defined by 24-hour impedance-pH monitoring, upper endoscopy or proton pump inhibitor test.

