### **7.4 Methods for statistical analyses**

#### **7.4.1 Analysis of the primary variable(s)**

The percentage of each symptom of GERD in the symptom questionnaire in Chinese outpatients in Gastroenterology department will be calculated. The symptom of the highest percentage will be the primary symptom.

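### The 0.045 precision in Section 7.1 belongs to GERD prevalence in all 400 patients; for the primary endpoint, symptom percentages in about 120 GERD patients, it is about 0.08–0.09

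*Combined protocol and SAP*

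**What the plan says.** Section 7.1 opens with "Assuming the prevalence of GERD is 30"% and goes on to say that "400 completed patients provides a precision (half width of 95% CI") "of 0.045 for the estimate of two-sided 95% confidence interval of the primary endpoint". The synopsis, under Statistical methods, makes the same claim: "Assuming the prevalence of GERD is 30%, 400 completed patients provides a precision (half width of 95% CI) of 0.045". No other precision or sample-size figure appears in the document.

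The primary objective in Section 2.1 is "To define the primary symptom of GERD in Chinese outpatients in Gastroenterology department". Section 7.4.1 sets out the primary analysis: "The percentage of each symptom of GERD in the symptom questionnaire in Chinese outpatients in Gastroenterology department will be calculated". It then applies a selection rule: "The symptom of the highest percentage will be the primary symptom".

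Section 3.1 admits consecutive clinic patients with upper gastrointestinal discomfort. Section 7.3 then classes as GERD those who are positive on impedance-pH monitoring, endoscopy or the PPI test. The GERD patients are therefore a subset of those enrolled. The outcome measures in Sections 2.1 and 2.2 do not include GERD prevalence.

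**The concern.** The sample-size sentence takes a prevalence as its input and attaches the resulting precision to a different quantity. Its arithmetic is correct, but the label is not. A prevalence among all completers has 400 in the denominator. A symptom percentage among GERD patients has only the GERD patients in the denominator, and a different proportion in the numerator.

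This figure is the only justification given for 400 patients. The primary result is a ranking of symptoms, and Section 1.1 raises the possibility that heartburn is not the leading reflux symptom in China. A reader who takes each symptom percentage to be known to within 4.5 points would give a small lead more weight than intervals of ±8 to 9 points can support.

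**Working it through.** **Inputs**

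- Assumed GERD prevalence: 0.30 (Section 7.1).
- Completed patients: 400 (Section 7.1). This is already a count of completers, so no dropout adjustment applies.
- Confidence level: 95%, two-sided, z = 1.96 (Section 7.1).
- Symptom frequency among GERD patients: not given, so a range is shown.

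**Formula:** half-width = z × √(p(1 − p)/n).

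**Step 1. Reproduce the stated figure.** With p = 0.30 and n = 400:

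1.96 × √(0.30 × 0.70 / 400) = 0.0449, which rounds to 0.045.

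The Wilson interval gives 0.0447 and Clopper-Pearson 0.0460. Solving for n at a half-width of 0.045 gives 398.4. The stated figure is therefore the half-width for GERD prevalence among all 400.

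**Step 2. Denominator of the primary endpoint.** Expected GERD patients = 0.30 × 400 = 120.

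**Step 3. Half-width for a symptom percentage with n = 120.**

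| Symptom frequency | Half-width | Wilson | Ratio to 0.045 |
|---|---|---|---|
| 10% | 0.054 | 0.054 | 1.2 |
| 20% or 80% | 0.072 | 0.071 | 1.6 |
| 30% or 70% | 0.082 | 0.081 | 1.8 |
| 40% or 60% | 0.088 | 0.086 | 1.9 |
| 50% | 0.089 | 0.088 | 2.0 |

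For example, at 50%: 1.96 × √(0.25/120) = 0.089. The half-width is at least 0.08 for any frequency from 28% to 72%.

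**Step 4. Sensitivity to the number of GERD patients.**

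| GERD prevalence | GERD patients | Half-width at 30% | Half-width at 50% |
|---|---|---|---|
| 30% | 120 | 0.082 | 0.089 |
| 40% | 160 | 0.071 | 0.077 |
| 50% | 200 | 0.064 | 0.069 |
| 60% | 240 | 0.058 | 0.063 |
| 70% | 280 | 0.054 | 0.059 |
| 100% | 400 | 0.045 | 0.049 |

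For symptom frequencies of 30–50%, the stated precision is approached only if nearly every completer has GERD.

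**Step 5. What 0.045 would need.** At a symptom frequency of 30%, 1.96² × 0.21 / 0.045² ≈ 398 GERD patients, or 398/0.30 ≈ 1,328 completers. At 50%, 1.96² × 0.25 / 0.045² ≈ 474 GERD patients, or about 1,581 completers. These numbers show the size of the gap and are not a proposal.

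**The case against.** **The denominator is not stated.** Section 7.4.1 speaks of percentages in outpatients and never says that they are taken among GERD patients. With all 400 as denominator, the half-width would be 0.045 to 0.049 at frequencies of 30–50%. If each percentage meant having both GERD and the symptom, it could not exceed 30%, and 0.045 would be an upper bound. The wording is indeed loose. However, no section states an all-patient denominator, the objective concerns the symptoms of GERD, and secondary objective 1, whose outcome measure is the same set of percentages, concerns patients with established pathologic reflux. If all 400 were intended, Section 7.1 would still have to say so.

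**The size is conditional.** The 0.08–0.09 range needs mid-range symptom frequencies, which the protocol does not supply. Rarer or near-universal symptoms have narrower intervals. This stands, and the figures are therefore given by frequency.

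**120 may be too few.** The definition is a composite of three tests. Section 1.1 reports pathologic acid reflux in about one third of dyspepsia patients without reflux symptoms, so the composite could well exceed 30%. Section 3.7 discontinues patients without relief at four weeks and Section 7.2.1 analyses per-protocol completers, which could raise the GERD share further. This also stands, but it would mean that the plan's 30% is itself wrong, and Step 4 shows the gap shrinking without closing.

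**Little depends on the figure.** The study is descriptive, and no decision rule uses 0.045, so correcting it changes neither the data nor the analysis. That is true. The sentence nevertheless makes an incorrect claim about the primary endpoint. It is also true that the precision of a single percentage does not measure how reliably the highest of several correlated percentages is identified. The correction below does not address that separate question.

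**Conclusion.** The concern holds. The stated 0.045 is a correct half-width for GERD prevalence, which is not an endpoint of this study, and the plan attributes it to the primary endpoint. On the plan's own 30% prevalence, and for symptom frequencies of 30–50%, the primary endpoint has a half-width of 0.082 to 0.089, or 1.8 to 2.0 times the stated value.

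The conclusion rests on GERD patients being the denominator, which is the reading that the objective and the GERD definition support. The size rests on about 120 GERD patients and on mid-range symptom frequencies. With 160 to 240 GERD patients the half-width at 50% is 0.077 to 0.063, still above 0.045.

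**What to change.** Replace the precision sentence in Section 7.1 and in the synopsis (Statistical methods) with text along these lines:

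> With 400 completed patients and an assumed GERD prevalence of 30%, about 120 GERD patients are expected. Symptom percentages will be calculated among GERD patients. For symptom frequencies of 30–50% (assumed), the half-width of the 95% confidence interval is about 0.08–0.09. The half-width for GERD prevalence itself is 0.045.

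If the investigators intended a different denominator, the same sentence should name it and give the matching precision.

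The cost is one restated passage in two places and a less favourable stated precision. No additional enrolment, data or change of analysis is requested. Edition 2.0 is dated June 2018 and the last subject was expected to complete in September 2018, so the practical aim is to have the correct figure on record before the symptom ranking is interpreted.
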